1 STUDY SUMMARY

Title	A Phase II Pilot Trial of Hydroxychloroquine, Everolimus or the Combination for Prevention of Recurrent Breast Cancer
Short Title	CLEVER Pilot Trial
Protocol Number	IRB #826253; UPCC 24116
Methodology	
This is a randomized, controlled, open label pilot trial. A total of 60 patients will be enrolled, with 15 patients allocated to each treatment arm. Patients will be evaluated at the initiation of every cycle for adverse events, and dose reduction will be employed for toxicity. Bone marrow aspiration will be performed at the end of cycle 3, cycle 6, and if patient continued on second treatment phase, at the end of cycle 12. The initial six-month study period is designed to assess the effects of HCQ, EVE and their combination. After three months of observation, control patients will be offered HCQ/EVE investigational therapy for six cycles; thus, the control group is actually a delayed treatment group and all patients will receive treatment. Patients who continue to demonstrate positive bone marrow DTCs after six cycles will be offered the opportunity to continue on combination therapy for an additional 6 cycles. Patients will continue to be followed for recurrence events for up to 3 years after completion of treatment.

Study Duration	Active Enrollment: 3 years; Follow-up: 3 years
Study Center(s)	The University of Pennsylvania and affiliated sites
Objectives	
Primary Clinical Objective: To evaluate the feasibility of administering HCQ, EVE or the combination in patients who have completed primary therapy for breast cancer and harbor bone marrow disseminated tumor cells
 
Endpoint: $\geq 75\%$ of patients in each arm reaching the 6-month evaluation time point without grade 3 or 4 toxicity.
 
Secondary Clinical Objectives:
 
1. To determine the safety of administering HCQ + EVE in combination with adjuvant endocrine therapy
 
Endpoints Incidence of adverse events within each treatment stratum and dose level by NCI CTCAE v4 criteria.
 
2. To evaluate preliminary efficacy of HCQ, EVE or the combination in reducing or eliminating DTCs
 
Endpoint

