	
discontinued for lack of feasibility, the trial may continue enrolling to those arms that remain feasible.
 
Toxicity will be assessed using NCI CTCAE v4 criteria. Patients who drop out before completing cycle 6 for reasons other than grade 3/4 toxicity will be replaced. With 15 patients per group, an exact 95% confidence interval around the feasibility and toxicity rates will be no more than 0.52 units wide.
 
We will define “response” for each patient as a 50% or greater decrease in DTC number at each treatment time point compared to baseline. A treatment arm/regimen will be considered successful if at least 3 of 15 of patients experience this predefined response endpoint.
 
We will also estimate, within each treatment group, the % change in DTC number. While the trial is powered for feasibility, rather than detection of change in DTCs across treatment group, 15 patients per group will provide 80% power (using a two-group t-test with a two-sided alpha level of 0.05) to detect a decrease of approximately 1 standard deviation and will provide important preliminary data for designing future confirmatory trials.

--	---

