11.2.2 Response Criteria

Response in this trial will be performed in all patients, and is defined by the change in detectable DTC number (# cell/5 ml marrow aspirate) from baseline to each timepoint. We will define “response” for each patient as a 50% or greater decrease in DTC number at each treatment time point compared to baseline. The interventional arm will be considered successful if at least 20% of patients experience this predefined response endpoint. We anticipate that the baseline variability in DTC measurement will lead to no more than a 4% response rate in the absence of treatment (null rate). The efficacy objective of this trial (a secondary objective) is to evaluate the preliminary efficacy of EVE, HCQ or the combination in reducing or eliminating breast cancer DTCs, and provide estimates of effect for future definitive trials. The primary measure of efficacy in this trial is change in the number of detectable disseminated tumor cells (DTCs) in the bone marrow of patients on study. DTCs will be detected from 5 ml of bone marrow extracted from the posterior iliac crest at baseline (pre-treatment), after 3 cycles, 6 cycles, and 12 cycles (if applicable) of study treatment, and at 6 months after the last dose of study treatment (optional).

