12.2 Analysis Plan

12.2.1 Primary Endpoint

The phase II trial endpoint “feasibility” is based upon the overall safety and tolerability of the treatment arms, and will be defined as at least 11 of 15 patients within each treatment group completing 6 cycles of therapy without grade 3 or 4 toxicity. When evaluating feasibility of the combination therapy, Arm C and D may be combined for analysis, since both arms receive the same study treatment (Arm D is just a delayed start). Toxicity will be determined by NCI CTCAE v4 criteria, and categorized by system and grade. Patients who drop out before the 6-month time

point for reasons other than toxicity and not related to feasibility will be replaced. With 15 patients per group, an exact 95% confidence interval around the feasibility and toxicity rates will be no more than 0.52 units wide. Arms that are discontinued for lack of feasibility will be dropped from the trial, but others may continue, so long as they remain “feasible” by this definition.

Because this is a potentially curable patient population, we will also institute an early stopping rule, should the toxicity rates exceed those expected or acceptable in this setting. To do this, we will implement a Bayesian toxicity monitoring approach with a target protocol-defined DLT rate of 30%. We assume a $Beta(1,2)$ prior, equivalent to one DLT observed in 3 treated patients. Early termination for toxicity will be considered based on a posterior probability that the toxicity rate exceeds 30%. Early termination will be considered if DLT is observed in 2 of 3 patients (0.84 posterior probability), 3 of 6 patients (0.81), 4 of 9 patients (0.79), 5 of 12 patients (0.78), 6 of 15 patients (0.78).

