12.2.2 Secondary Endpoints

The secondary endpoints are tolerability/toxicity and the measured effect of the investigational therapy on DTCs in patients with measureable DTCs at baseline and the comparison of this effect to that in a control population. Because this is proof-of-concept, sample sizes are not sufficient to address long-term recurrence risk. Randomization is being performed to minimize uncontrolled confounding.

We will define “response” for each patient as a 50% or greater decrease in DTC number at each treatment time point compared to baseline. A treatment arm will be considered successful if at least 3 of 15 patients experience this predefined response endpoint. This strategy is being used to provide preliminary estimates of effect on DTCs and to assess whether one or more treatment approaches has sufficient activity to be considered in a larger study powered for relapse-free survival. We anticipate that the baseline variability in DTC measurement will lead to no more than a 4% response rate in the absence of treatment (null rate). While the trial is powered for feasibility, 15 patients provide approximately 80% power to detect a response rate of 20%, warranting further study of the treatment strategy evaluated in this patient population and clinical setting.

We will also estimate, within each treatment group, the % change in BM-DTC number, defined as the difference between BM-DTCs enumerated at 6 months and at baseline, divided by the number at baseline; we will compare this quantity across treatment groups using simple regression analyses with indicator variables for the three active treatments compared to the delayed treatment. While the trial is powered for feasibility, rather than detection of change in BM-DTCs across treatment group, 15 patients per group will provide 80% power (using a two-group t-test with a two-sided alpha level of 0.05) to detect a decrease in BM-DTCs of approximately 1 standard deviation between any two groups and will provide important preliminary data for designing future trials.

Because of tumor heterogeneity, the natural history of recurrence varies substantially between breast cancer subtypes. We have elected not to expand the

sample size to evaluate subtypes individually in this feasibility pilot, but expect that we will enroll a mix of patients across subtypes that will shed light on variability in DTCs by subtype in an exploratory fashion.

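### The claimed 80% power to detect a 20% DTC response rate does not belong to the protocol's rule of at least 3 responders in 15; the exact power is 60%

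*Protocol*

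**What the plan says.** Protocol section 12.2.2 gives all the inputs in one paragraph. Response is defined patient by patient: "We will define “response” for each patient as a 50% or greater decrease in DTC number at each treatment time point compared to baseline". The decision rule is "A treatment arm will be considered successful if at least 3 of 15 patients experience this predefined response endpoint". The rate expected without treatment is at most 4%. The power claim follows: "15 patients provide approximately 80% power to detect a response rate of 20" percent.

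The rule appears in two other places. The Study Summary (section 1, Statistical Methodology) has "A treatment arm/regimen will be considered successful if at least 3 of 15 of patients experience this predefined response endpoint". Section 11.2.2 puts the threshold as a percentage, "The interventional arm will be considered successful if at least 20% of patients experience this predefined response endpoint", which for 15 patients is again 3, and repeats the 4% null rate. The arm size comes from the Study Summary: "A total of 60 patients will be enrolled, with 15 patients allocated to each treatment arm".

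No significance level, sidedness or test is named for this power figure. The other 80% figure in section 12.2.2 concerns a two-group t-test on percent change in DTC count, which is a different analysis. The SAP text describes a Bayesian Poisson model for DTC counts and gives no operating characteristics for the 3-of-15 rule.

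**The concern.** Once the number of patients and the cut-off are fixed, the power at a given true rate is one binomial tail probability, with nothing left to choose. For 15 patients at a true rate of 20% the expected number of responders is 15 × 0.20 = 3, exactly the cut-off. A rule that requires the observed count to reach its own expected value will fail often, so 80% looked too high.

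Section 12.2.2 uses the response rule to label each regimen successful or not, and to judge whether it has enough activity to be considered for a larger study powered for relapse-free survival. A reader who trusts 80% power will take an arm with 0, 1 or 2 responders as fairly strong evidence against 20% activity. If the power is much lower, that reading is too confident, and the risk applies to each regimen separately.

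**Working it through.** **Inputs**

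- n = 15 per arm (Study Summary; section 12.2.2)
- Success if X ≥ 3 (section 12.2.2; Study Summary; equal to 20% in section 11.2.2)
- Null rate p0 = 0.04 (sections 11.2.2 and 12.2.2)
- Target rate p1 = 0.20 and stated power about 0.80 (section 12.2.2)
- X is binomial(15, p), where p is the per-patient probability of meeting the response endpoint at the deciding assessment

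**Step 1. Try to reproduce the stated figure with the stated rule**

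P(X ≥ 3) = 1 − P(0) − P(1) − P(2).

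At p = 0.20:

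- P(0) = 0.8^15 = 0.0352
- P(1) = 15 × 0.2 × 0.8^14 = 0.1319
- P(2) = 105 × 0.2² × 0.8^13 = 0.2309
- Sum = 0.398, so power = **0.602**

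At p = 0.04:

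- P(0) = 0.96^15 = 0.5421
- P(1) = 15 × 0.04 × 0.96^14 = 0.3388
- P(2) = 105 × 0.04² × 0.96^13 = 0.0988
- Sum = 0.9797, so the false-positive probability = **0.0203**

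The stated 80% is not reproduced; the gap is about 20 percentage points.

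**Step 2. Look for another route to 80%**

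| Calculation | Power at 20% | False-positive probability or alpha |
|---|---|---|
| Exact, ≥ 2 of 15 | 0.833 | 0.119 at p = 0.04 |
| Exact, ≥ 3 of 15 (the rule) | 0.602 | 0.020 at p = 0.04 |
| Exact, ≥ 4 of 15 | 0.352 | 0.002 at p = 0.04 |
| Normal (score) approximation | 0.771 | one-sided 0.05 |
| Normal (score) approximation | 0.822 | one-sided 0.10 |
| Normal (score) approximation | 0.801 | two-sided 0.15 |
| Two groups of 15, 4% vs 20% | 0.264 | two-sided 0.05 |
| Two groups of 15, 4% vs 20% | 0.380 | one-sided 0.05 |

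The score approximation is Φ{[√n(p1 − p0) − z√(p0(1 − p0))] / √(p1(1 − p1))}. At one-sided 0.05 this is Φ{[0.6197 − 1.645 × 0.1960] / 0.4} = Φ(0.743) = 0.771.

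An exact one-sided test of 4% with 15 patients has cut-off 3 at alpha 0.025, 0.05 and 0.10 alike, because a cut-off of 2 already costs 0.119. Exact power is therefore 60.2% at each of those levels.

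**Step 3. What would give 80% with a cut-off of 3**

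- n = 15: the true rate must be about 26.4% (power 0.790 at 26%, 0.814 at 27%).
- True rate 20%: n = 21 is needed (power 0.821, false-positive probability 0.0497); n = 20 gives 0.794.

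**Step 4. Power of the stated rule at other true rates**

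| True response rate | Power, ≥ 3 of 15 |
|---|---|
| 20% | 0.602 |
| 25% | 0.764 |
| 30% | 0.873 |

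**Step 5. Pooling Arms C and D**

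The protocol allows pooling for the primary endpoint: "When evaluating feasibility of the combination therapy, Arm C and D may be combined for analysis". It does not say this for response. If response were pooled too, and the group were 30 (an assumption), the 20% threshold becomes 6 of 30 and power at 20% is 0.572. Pooling under the percentage rule does not restore the figure.

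**The case against.** The arithmetic cannot be disputed, but four points can fairly be made.

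First, response is a secondary endpoint and the protocol says plainly that the trial is powered for feasibility. The sample size, the decision rule and the primary analysis do not depend on the 80% figure. This stands, and it limits the consequences.

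Second, the 40% miss rate holds only at a true rate of exactly 20%. For more active regimens the rule does better, as Step 4 shows. This stands as a qualification, but 20% is the rate at which the protocol itself quotes the power.

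Third, the power sentence names no test or alpha, and an uncorrected normal approximation comes close to 80% at some levels. That may be where the figure came from, though the documents do not say. It does not defend the sentence: the rule is a count, its power can be computed exactly, and the approximation describes a different procedure.

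Fourth, the protocol does not say that an arm is dropped for missing 3 of 15; its arm-dropping rule concerns feasibility. DTC activity is also examined through percent change and, in the SAP, through a Poisson model with credible intervals. Over-interpretation of a negative arm is therefore a risk rather than a certainty. But the protocol does label arms successful by this rule and ties the label to further study, so the power attached to it matters.

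**Conclusion.** The power statement in section 12.2.2 is wrong as written. Under the protocol's own rule, power at a 20% response rate is 60.2%, not about 80%, and the chance of calling such a regimen unsuccessful is 39.8%, about twice what the text implies. The false-positive probability at the 4% null rate is 2.0%.

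This rests on 15 patients per arm, independent patients, and 20% as the per-patient probability of meeting the response endpoint at one deciding assessment. The last is an assumption, because the definition refers to every treatment time point without saying which one, or whether any or all, decides success. The error affects how each arm's DTC result is read; it does not touch the primary feasibility endpoint.

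**What to change.** In section 12.2.2, replace the power sentence with the exact operating characteristics, for example:

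> With 15 patients, requiring at least 3 responders gives 60% power if the true response rate is 20%, a 2% chance of declaring success if the true rate is 4%, and about 80% power if the true rate is 26–27%.

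Keep the sample size and the rule. The sentence applies to 15 patients only. Section 7 plans at least 15 per treatment group and treats Arms C and D as one group, so if response is to be judged on a larger combination group, give the cut-off and its exact power for that number as well. It would also help to name the assessment that decides success.

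The cost is one sentence of protocol wording and a less favourable stated power. No extra patients are needed and trial conduct does not change.

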2.2 Secondary Clinical Objectives

2.2.1 To determine the safety of administering HCQ + EVE in combination with adjuvant endocrine therapy

Endpoints

- Incidence of adverse events within each treatment stratum and dose level by NCI CTCAE v4 criteria.

2.2.2 To evaluate preliminary efficacy of HCQ, EVE or the combination in reducing or eliminating DTCs

Endpoints

- Change in bone marrow DTCs at 3, 6 and 12 months of treatment relative to baseline (pre-treatment)
- Change in bone marrow DTCs at 3 months with no treatment (Arm D Control) compared to any treatment (Arms A, B or C)
- Incremental benefit of an additional 6 months of therapy in patients who have DTCs after initial 6 months of therapy
- Incremental benefit of combination therapy compared to single-agent therapy

2.2.3 To estimate the risk of recurrence after treatment with HCQ, EVE, or the combination

Endpoint

- 3-year recurrence free survival (RFS)

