7 TREATMENT PLAN

This is a randomized, controlled, open label pilot trial. A total of 60 patients

will be enrolled, with at least 15 patients allocated to each treatment group (Arms C and D constituting the same treatment group). The initial treatment period is 6 months (24 weeks). During the initial treatment period, patients will be randomized to one of 4 arms: HCQ alone (Arm A), EVE alone (Arm B), combination HCQ and EVE (Arm C) – Arm C is closing to accrual with Amendment 7 – or control/delayed combination HCQ and EVE (Arm D). Starting with Amendment 7, patients who would have been allocated to Arm C will be redirected to Arm D in order to increase the number of patients with repeat DTC assessments to aid assay reproducibility analysis. At the conclusion of 3 cycles of therapy (Arms A, B, and C) or 3 cycles of observation (Arm D), patients will undergo repeat bone marrow aspirate. Patients on Arm D will then commence combination therapy with HCQ + EVE for 6 cycles (24 weeks). After 3 cycles of therapy, patients on Arm D will undergo another bone marrow aspirate. After 6 cycles of therapy, patients on all arms will undergo another bone marrow aspirate. Patients with a negative bone marrow aspirate for DTCs at after cycle 6 will have all therapy discontinued and enter the follow up phase. Patients who have persistently positive bone marrow DTCs will be continued on combination HCQ + EVE for an additional 6 cycles (24 weeks). At the conclusion of this combination treatment period (cycle 12), all treatment will be discontinued and a bone marrow aspirate will be performed.

Patients will be evaluated at the initiation of every cycle for adverse events, and dose reductions will be employed for toxicity. Patients will continue to be followed for recurrence events for 3 years after completion of treatment.

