7.1 Study Arms

Patients will be randomized during the Screening Phase to one of four investigational arms. These are shown in the schema above and detailed as follows (Note that Arm C is closing with Amendment 7):

Arm A: Patients will receive HCQ, 600 mg BID, for 24 weeks. If they are determined to have detectable DTCs after week 24, they will be crossed over to combination therapy, in which they will continue HCQ, 600 mg BID and add EVE, 10 mg daily for an additional 24 weeks.

Arm B: Patients will receive EVE, 10 mg daily, for 24 weeks. If they are determined to have detectable DTCs after week 24, they will be crossed over to combination therapy, in which they will continue EVE, 10 mg daily and add HCQ, 600 mg BID, for an additional 24 weeks.

Arm C: Patients will receive the combination of HCQ, 600 mg BID, and EVE, 10 mg daily, for 24 weeks. If they are determined to have detectable DTCs after week 24, they will continue combination HCQ/EVE therapy for an additional 24 weeks. Arm C is closing with Amendment 7. Patients randomized after Amendment 7 who would have been assigned to Arm C will be redirected to Arm D.

Arm D: Patients will be observed for 12 weeks without study therapy. At the completion of the observation period, they will receive combination therapy of HCQ, 600 mg BID and EVE, 10 mg daily for 24 weeks. If they are determined to have detectable DTCs after week 24, they will continue combination HCQ/EVE therapy for an additional 24 weeks.

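### The 6-month DTC regression in protocol 12.2.2 uses a reference arm that is already on HCQ + EVE; the control comparison belongs at 3 months, and the protocol and SAP must be reconciled on it

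*Protocol*

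**What the plan says.** - **Protocol 12.2.2** bases percent change on "the difference between BM-DTCs enumerated at 6 months and at baseline", divided by the baseline count. It compares this across groups by regression with "indicator variables for the three active treatments compared to the delayed treatment". The same section names comparison with a control population as part of the secondary endpoint.
- **Protocol 7.1**, on Arm D: "Patients will be observed for 12 weeks without study therapy". Sections 7 and 7.1 then give Arm D HCQ + EVE for 24 weeks. The Study Summary says that "the control group is actually a delayed treatment group and all patients will receive treatment".
- **Protocol 2.2.2** lists an untreated contrast as an endpoint of its own: "Change in bone marrow DTCs at 3 months with no treatment (Arm D Control) compared to any treatment (Arms A, B or C"). It also lists change at 3, 6 and 12 months of treatment.
- **Protocol 7**: "Arm C is closing to accrual with Amendment 7". Patients who would have gone to Arm C are sent to Arm D from then on.
- **SAP, Bayesian Poisson regression model**: treatment effects for HCQ, EVE and HCQ + EVE are given by visit as a percent reduction in mean DTCs relative to observation alone at C3.

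**The concern.** A regression against a control arm is useful only if that arm is untreated when the outcome is measured. At 6 months Arm D is not. The only randomised untreated period ends at week 12, and 12.2.2 places its between-group comparison after it.

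At stake is the part of the secondary objective that asks how DTC change on treatment compares with change in a control population. Section 12.2.2 says that these estimates will inform future trials. A treated reference would understate the effect of each regimen. It could also make a single agent look worse than control when it is merely less active than the combination. A reader of both documents would also find two different comparators for one endpoint.

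**Working it through.** **1. The plan's own power figure.** Section 12.2.2 states 80% power for about 1 SD with 15 per group, using a two-group t-test at two-sided 0.05. The normal approximation gives 78% at exactly 1 SD. The non-central t (28 df) gives 75% at exactly 1 SD and reaches 80% at 1.06 SD. The stated figure is therefore reproduced.

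**2. What Arm D has received at each aspirate.** Sections 7, 7.1 and 7.2 give 28-day cycles, with 6 months equal to 24 weeks. Weeks are nominal and counted from randomisation.

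| Week | Arms A, B, C | Arm D |
|---|---|---|
| 12 | after 3 cycles of assigned regimen | end of observation, untreated |
| 24 | after 6 cycles | 24 − 12 = 12 weeks, or 3 cycles, of HCQ + EVE |
| 36 | no aspirate scheduled | 36 − 12 = 24 weeks, or 6 cycles, of HCQ + EVE |

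If 6 months runs from randomisation, 6 cycles of each active regimen are compared with 3 cycles of the combination. If it means 6 months of treatment, as 2.2.2 words its change endpoint, the reference is 6 cycles of the combination, and Arm C versus Arm D compares a regimen with itself. Only week 12 gives an untreated reference.

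**3. What that does to the contrast.** Suppose a regimen's true effect against no treatment is 1 SD and Arm D already shows a fraction f of it. The expected difference is (1 − f) SD. The documents give no value for f, so these are assumptions:

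| f | Difference (SD) | Power, 15 v 15 |
|---|---|---|
| 0 | 1.00 | 75% |
| 0.25 | 0.75 | 51% |
| 0.50 | 0.50 | 26% |
| 0.75 | 0.25 | 10% |

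If f exceeds 1, because the combination outperforms a single agent, the sign reverses.

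**4. The 3-month contrast of 2.2.2.** Arms A + B + C (45) against untreated Arm D (15), by t-test at two-sided 0.05, has 91% power at 1 SD and 80% power at 0.85 SD.

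**5. SAP figures after C3.** If the true reduction against a concurrent untreated group is e, and untreated counts would have fallen by a fraction r after C3, the reduction read against the C3 value is 1 − (1 − e)(1 − r). This equals e only when r = 0. The documents give no rate of untreated change after C3.

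**6. Amendment 7.** The number enrolled in Arm C is not given. For illustration, assume 15 in each of A and B, 30 in C + D together, and c in each arm before the amendment. Then C = c, D = 30 − c, and 30 − 2c of Arm D enrolled afterwards. Also assume a 0.5 SD shift between enrolment periods. Unadjusted bias is 0.5 × the difference in post-amendment shares.

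| c | Post-amendment share of D | Share of A + B + C | Bias, pooled | Bias, C v all D | Power at 1 SD, pooled |
|---|---|---|---|---|---|
| 5 | 20/25 = 0.80 | 20/35 = 0.57 | 0.11 SD | 0.40 SD | 96% |
| 8 | 14/22 = 0.64 | 14/38 = 0.37 | 0.13 SD | 0.32 SD | 96% |
| 10 | 10/20 = 0.50 | 10/40 = 0.25 | 0.13 SD | 0.25 SD | 95% |

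Restricting Arm C to its concurrent Arm D patients (c v c) leaves 29%, 46% or 56% power at 1 SD.

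**The case against.** The strongest reply is that the SAP has already dealt with this. Its model has treatment-by-visit effects and takes observation alone at C3 as the reference. That is the untreated contrast, arm by arm, and the SAP is written as an analysis already carried out. On this view only a mismatch of wording remains, on a secondary endpoint that the protocol says it is not powered for.

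Much of this stands. A reader of 12.2.2 alone might infer that the documents contain no analysis against untreated patients; the SAP shows otherwise. One might also suspect that Arm D's on-treatment visits leak into the control group. Nothing in the SAP suggests that: it keeps observation at C3 apart from HCQ + EVE. What does not stand is that the matter is closed. The SAP text does not withdraw the 6-month regression, and it does not give the pooled any-treatment contrast of 2.2.2.

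On the later visits, the SAP names its reference visit openly, and read purely as a description relative to C3 the figures assume nothing. They need the no-change assumption only when read as treatment effects, which is what the SAP calls them. A label is enough.

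On Amendment 7, it is tempting to say that Arm C lacks a concurrent randomised comparator. That is wrong: every Arm C patient was randomised while Arm D was open. The problem is only that part of Arm D enrolled after Arm C closed. The pooled contrast of 2.2.2 is also much less exposed than Arm C alone.

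**Conclusion.** The point holds and should be fixed. As written, the 12.2.2 regression has no untreated reference on either reading of 6 months. This follows from the protocol's own schedule and needs no outside figure. The direction, toward zero with possible reversal, assumes only that the combination lowers DTCs.

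The amount of dilution is not known. The power figures under partial carry-over rest on assumed fractions and show how the loss grows, not how large it is here. The Amendment 7 figures likewise rest on assumed arm sizes and an assumed period shift; the documents do not allow that effect to be sized.

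Two wider inferences should be resisted. The 75% power at exactly 1 SD does not show the protocol's 80% to be wrong, because the protocol says approximately 1 SD. Nor does the point reach the main conclusions: the feasibility endpoint and the within-arm rule of 3 responders in 15 do not use this contrast.

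**What to change.** 1. **Protocol 12.2.2:** make the control comparison the change from baseline to 3 months (end of C3 for Arms A to C, end of observation for Arm D). Give it pooled, as 2.2.2 lists it, and by arm. Use 6-month values only to compare HCQ, EVE and the combination with each other.
2. **SAP:** name the C3 contrast as the control comparison, so that both documents agree. Label figures against observation at later visits as non-concurrent and as assuming no untreated change after C3.
3. **Amendment 7:** include a before/after-amendment term in the control contrasts, including the pooled one. Alternatively, restrict Arm C versus observation to patients randomised before the amendment as a sensitivity analysis. Report the arm sizes at the amendment.

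**Cost:** no new aspirates or visits, since the end-of-C3 and end-of-observation samples are already scheduled. There is a little more analysis work, and the later figures against observation are relabelled. If the restricted Arm C comparison is used, it may be small enough to be descriptive only.
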